2. Patients receiving treatment with specific anti-osteoporosis medication (denosumab/bisphosphonates) (because of the profound effect on calcium/phosphate fluxes and BMD)

Withdrawal from intervention but continued follow-up (included in intention-to-treat analysis)

1. Withdrawal of consent
2. Kidney transplantation

3. Parathyroidectomy
4. Necessity to initiate dialysis treatment

Patients may withdraw from both intervention and follow-up at any time if desired.

Study design

The REPAIR-CKD trial will be an investigator-initiated pragmatic randomized controlled clinical trial. Included patients will be randomized 1:1 into one of two treatment arms with different targets levels for plasma-PTH: A liberal PTH target ($< 5 \times$ upper normal limit = 42,5 $\mu\text{mol/L}$) or an intensive PTH target (within interval of lower and upper normal limits = 2,0 – 8,5 $\mu\text{mol/L}$) (Figure 1). The cut-off for the liberal PTH target ($< 5 \times$ upper normal limit) was discussed in the national CKD-MBD group. It is chosen to allow the clinician initiate treatment if PTH reaches unusually high levels, no studies have focussed on PTH-targets before, consequently the cut-off is chosen as part of the pragmatic design.

The trial will also pilot the feasibility to obtain a difference in the PTH levels between treatment groups.

[figure not shown]

Figure 1. Visit overview.

Sample size

The primary outcome will be difference in the change in total hip BMD between treatment groups.

In an observational study, the decline in total hip BMD (g/cm^2) was $-1.19\%/\text{year}$ (men) and $-1.51\%/\text{year}$ (women). The decline in men is chosen for a conservative estimate (36). In the dialysis population, the standard deviation (SD) of the one-year decline in BMD is $\pm 5.2\%$ (37). The variance in the BMD change in dialysis patients is expected to be higher than in the CKD population, and therefore this is considered a conservative estimate. Based on these observations the expected decline in BMD in the liberal target group during 18 months is -1.8% (5.2%).

In a previous trial, alendronate was able to increase BMD in total hip by 2.8% during the first year of treatment and 3.4% during 2 years treatment, and thus to increase BMD by 3.1% in 18 months (38). We expect to obtain a similar effect in the intensive target group.

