A sample size of 70 participants is estimated ($\beta=0.10$; $\alpha=0.05$ (two-sided), drop out 20 % during the study) to detect a difference of 4.9 % change in total hip BMD (effect size) during 18 months.

To ensure that the trial can also provide information about the other fields of interest, we did some statistical considerations about these as well. A minimal relevant difference in the level of PTH after 18 months of intervention is expected to be a difference in PTH of 0.5 times the upper limit of normal range ($8.5 \mu\text{mol}/\text{L}$ (Atellica IM PTH)). PTH has a skewed distribution and thus log transformed to obtain normality. In a population of patients with CKD G4-5 the mean and standard deviation of the logPTH was 1.191 (0.380) (own data, not published). To obtain a difference of 4.25 $\mu\text{mol}/\text{L}$ in PTH = logPTH of 0.628 ($(\beta=0.10$; $\alpha=0.05)$ a sample size of 22 participants is estimated (including drop-out margin of 20%). Based on former studies the sample size should be sufficient to demonstrate a difference of 1 m/s in pulse wave velocity which is considered a difference of clinical relevance for future cardiovascular events(39).

Interventions

The trial is estimated to run for 24 months, as patients will be included during a 6-months period following 18 months follow-up. Following inclusion there will be a 4 weeks run-in period where patients will not be treated with active vitamin D or calcimetics. After run-in patients will be

randomized to either a liberal PTH target ($< 5 \times$ upper normal limit = 42,5 $\mu\text{mol/L}$) or an intensive PTH target (within interval of lower and upper normal limits = 2,0 – 8,5 $\mu\text{mol/L}$). In the intensive PTH target group, treatment will be initiated as soon as the PTH rise above the upper limit of normal. In the liberal PTH target group, treatment will not be initiated until PTH rise above five times the upper limit of normal.

PTH will be measured as intact PTH with Atellica IM PTH assay at Herlev Hospital laboratory (normal range 2,0 – 8,5 $\mu\text{mol/L}$).

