Volume of the standard blood samples at each visit is 16 ml. Further there will be drawn 14 ml at baseline visit and 18-months visit for the research biobank and 18 ml once for the biobank for future research (discussed in more details in p. 14 “Biobank for future research”). Maximal volume blood drawn at once is 48 ml (baseline visit). Total amount of blood drawn in the study will not exceed 200 ml.

DXA-scan

DXA-scan will be used to measure BMD (amount of calcium and phosphate per area in g/cm² followed by calculation of T-score) in lumbar spine, left hip (if not applicable, then right) and non-dominant forearm (if not with a fistula). Whole body scan will be performed to measure whole-body BMD and appendicular lean body mass as an approximation of muscle mass. Additionally, vertebral fracture assessment (VFA) will be performed to assess any fractures in lumbar spine. Efforts will be made to optimize that baseline and follow-up procedure will be performed by the same person to minimize interobserver variance. The research laboratory at Herlev Hospital has research staff and DXA-scan (Hologic Horizon, 2021-2022) for performing the measures. The above-mentioned procedures will be carried out after validation on a spine phantom performed daily and calibration of body composition takes place simultaneously (Refer to the Horizon User Guide (MAN-08072-002) for operating instructions). All patients included will have a DXA-scan at day 0 and at 18 months.

Bioimpedance

Body composition parameters, including segmental lean mass (arms, legs, trunk), skeletal muscle mass, fat-free mass, and body fat percentage, will be measured at baseline and 18 months follow-up by bioelectrical impedance analysis (BIA; multi-frequency InBody 570).

Pulse wave velocity

Pulse wave velocity will be assessed at day 0 and at 18 months by applanation tonometry with Sphygmocor. Pulse wave analysis is a non-invasive way of estimating to which extent peripheral reflection is augmenting central blood pressure. Pulse wave velocity is a direct measure of arterial stiffness. This procedure will be performed in accordance with a standard operating procedure and in accordance with guidelines from DaHS (Danish Hypertension Society). The Sphygmocor exists at the research laboratory at Herlev Hospital.

Muscle strength and function

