PTH is routinely measured in the clinic and blinding is not feasible as unblinding of the allocated treatment group will easily occur. The open-label design may influence the adherence, as the treating physician or the patient may favour a specific PTH target. It is therefore of great importance to monitor the adherence to the allocated treatment target through levels of PTH, and doctors as well as participants will be encouraged to comply.

The DXA-scan and analysis of this will be blinded, as the investigator performing the intervention will not perform the scans.

Efficacy endpoints

Primary endpoint:

Difference in % change in bone mineral density (BMD) between the treatment groups.

This is the generally accepted outcome for trials comparing treatment effects on BMD.

Secondary endpoints:

- Difference in follow-up BMD between treatment groups
- Difference in follow-up arterial stiffness between the treatment groups
- Differences in follow-up muscle mass between the treatment groups
- Differences in follow-up muscle function between the treatment groups
- Differences in bone histology between the treatment groups
- Differences in follow-up health-related quality of life between the treatment groups
- Differences in number of spinal fractures between the treatment groups

The feasibility to obtain a differential PTH level of at least 0.5 times the upper limit of normal between the two groups will be determined. During the piloting the number of withdrawals of consent and crossovers will be determined to improve the set-up, to increase retention and adherence and adjust the sample size estimation.

Adverse events

All serious adverse events (SAE) will be recorded during trial period. SAE is any case of death, life threatening event, persistent or significant disability, hospitalisation, prolongation of existing hospitalisation or treatment necessary to avoid the above and congenital anomaly/birth defect. It is the responsibility of the investigator to assess whether any SAE is with reasonable possibility causally related to the study intervention. Within 7 days after becoming aware of a SAE, the investigators will report these to the local scientific ethics committee. Once annually the primary investigator will report a summary of SAEs to the local scientific ethics committee.

All cases of hyper/hypocalcaemia and hyperphosphatemia will be registered as adverse events of interest.

Statistics

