All included participants will be accounted for and presented in a CONSORT diagram.

Baseline characteristics will be presented as mean \pm standard deviation or median and interquartile range, and number and percentages.

The primary endpoint % change in BMD during 18 months will be compared between groups with unpaired t-test.

This will be further explored by comparison of BMD after 18 months by ANCOVA adjusted for baseline BMD.

For secondary outcomes with a baseline and a single follow-up measurement, comparison between treatment groups will be performed by ANCOVA, adjusted for the baseline value. If more suitable, this analysis will be done with mixed effect model.

Secondary outcomes with baseline and multiple post-randomization measurements will be compared as baseline-adjusted follow-up values using a mixed model repeated measures approach.

Categorical outcomes will be compared by Chi²-test. Continuous outcomes will be presented as graphs of means and standard error of the means at each time point. Continuous outcomes with non-normal distribution will be logarithmic transformed to obtain normality before analysis.

Two-sided P-values < 0.05 is considered statistically significant.

All data will be described including data-incompleteness as well as reasons for data-incompleteness. Imputation will be used, if reasonable, to manage data-incompleteness in the analyses.

Analyses will be run in R studio, SAS and STATA. A statistical analysis plan will be decided before data lock.

Time schedule

The study will not be initiated until approved by the local scientific ethics committee, expected in summer of 2025. Recruitment is expected to last 6 months followed by 18 months follow-up. The study period will last 18 months for each patient.

Rights and publication

Principal investigator [name] will coordinate the study. [name] will be first author on any subsequent publications.

[name] will be final author on any subsequent publications.

Authorship will be granted to any person who contribute to the subsequent publications according to the Vancouver Guidelines.

All results, either positive, negative or inconclusive, will be submitted for publication in peer-reviewed journals.

Ethics

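### The deciding test of % change in total hip BMD leaves out baseline BMD, although the protocol scans everyone at baseline and adjusts for baseline in its follow-on and single-follow-up analyses

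*Protocol*

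**What the plan says.** Four statements in the protocol's Statistics section matter here.

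- Primary endpoint: "The primary endpoint % change in BMD during 18 months will be compared between groups with unpaired t-test". No covariate is named.
- Follow-on analysis: "This will be further explored by comparison of BMD after 18 months by ANCOVA adjusted for baseline BMD".
- Secondary outcomes with a baseline and one follow-up value: "comparison between treatment groups will be performed by ANCOVA, adjusted for the baseline value", with a mixed effect model allowed if it suits better. Outcomes measured repeatedly are also compared as baseline-adjusted values.
- Non-normal data: "Continuous outcomes with non-normal distribution will be logarithmic transformed to obtain normality before analysis". No exception is given for outcomes that can be zero or negative.

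Baseline BMD will be available. The DXA-scan section says: "All patients included will have a DXA-scan at day 0 and at 18 months". The Efficacy endpoints section says of % change in BMD: "This is the generally accepted outcome for trials comparing treatment effects on BMD". The Sample size section plans the trial on the same scale, "to detect a difference of 4.9 % change in total hip BMD (effect size) during 18 months", and names the total hip as the site.

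**The concern.** The baseline-adjusted analysis of BMD is placed second, as exploration, and the unadjusted one decides the trial. The protocol gives no reason for this, and it adjusts its other continuous outcomes that have a baseline.

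Baseline BMD is the denominator of % change and also enters its numerator. Measurement error in the baseline scan alone therefore tends to make the correlation between baseline and % change negative. In a small trial, and with no stratification by BMD mentioned in the Randomisation section, the arms may differ at baseline by chance. If they do and the correlation is not zero, part of that difference appears in the unadjusted estimate as if it were treatment effect. A covariate removes it, using data already collected.

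The log-transform sentence is a lesser matter. It is worded for all continuous outcomes, so on a literal reading it reaches % change, and negative values have no logarithm.

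**Working it through.** **Inputs from the Sample size section.** Expected 18-month change is -1.8% (SD 5.2%) in the liberal arm and +3.1% in the intensive arm, so the difference is 3.1 + 1.8 = 4.9 points. Two-sided alpha is 0.05, power 90%, dropout 20%, N = 70, allocated 1:1. Completers: 70 × 0.8 = 56, or 28 per arm.

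**Assumptions.** SD 5.2 in both arms. The correlation rho between baseline BMD and % change is not in the documents and is taken as -0.03, -0.10, -0.17 and -0.26.

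**The plan's own figure.** The stated inputs give 24 per arm by the normal approximation (48 / 0.8 = 60) or 25 per arm by the exact t-test (50 / 0.8 = 62.5, so 63, or 64 with equal arms). The stated 70 is not reproduced but is larger than needed. That is a separate matter. With 28 completers per arm, the exact t-test has 93.4% power at 4.9 points.

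**Chance imbalance at baseline.** In SD units, the standard error of the baseline difference is sqrt(2/28) = 0.267. An imbalance of 0.3 SD or more in either direction has probability 2 × [1 - Phi(0.3/0.267)] = 0.26.

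**Effect on the unadjusted estimate.** Shift = |rho| × 5.2 × 0.3 points. The standard error of the treatment difference is 5.2 × sqrt(2/28) = 1.39 points.

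**Precision and power with adjustment.** Variance of the adjusted relative to the unadjusted estimate: (1 - rho²)(1 + 1/52). Power comes from 60,000 simulated trials per setting at a true difference of 4.9.

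| rho | Shift, points | Shift as share of 4.9 | Shift in standard errors | Variance ratio | Power, t-test | Power, ANCOVA |
|---|---|---|---|---|---|---|
| -0.03 | 0.05 | 1% | 0.03 | 1.018 | 93.4% | 92.9% |
| -0.10 | 0.16 | 3% | 0.11 | 1.009 | 93.3% | 93.0% |
| -0.17 | 0.27 | 5% | 0.19 | 0.990 | 93.2% | 93.5% |
| -0.26 | 0.41 | 8% | 0.29 | 0.950 | 93.3% | 94.4% |

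Adjustment improves precision only when |rho| exceeds sqrt(1 - 1/(1 + 1/52)) = 0.137. Simulated type I error was 0.049 to 0.050 for both analyses. They disagreed on significance in 1.3 to 2.8% of trials at 4.9 points, and in 3.7 to 8.8% at half that difference.

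**Log-transform rule.** With normal distributions and the planning figures, the share of negative values is Phi(1.8/5.2) = 0.64 in the liberal arm (about 18 of 28) and Phi(-3.1/5.2) = 0.28 in the intensive arm (about 8 of 28). The chance that all 56 values are positive is about 6 × 10^-17.

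**The case against.** The strongest reply is that this is a choice between two valid analyses. The t-test is named in advance, is unbiased under randomisation, and matches the endpoint and scale on which the sample size was set. Its confidence interval already allows for chance imbalance, and the shift is at most 0.29 standard errors over the assumed range. At two of the four assumed correlations the adjusted analysis is slightly less precise. A baseline-adjusted analysis of 18-month BMD will be reported anyway. The secondary outcomes are follow-up values, which need baseline as a covariate to use it at all, whereas % change already contains baseline; different handling is not a contradiction.

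Most of this stands, and it limits the point. What remains is that dividing by baseline does not remove correlation with it, and that the planned follow-on analysis is on a different scale and does not decide the trial.

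A reader might infer three stronger things, none of which the documents support:

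- That the t-test is invalid or biased. It is not, and type I error is at its nominal level.
- That the trial gives up material power. Power differs by about one point or less over the assumed range, and no correlation is documented that would justify a larger claim. Disagreement between two valid tests does not show that the t-test is the wrong one.
- That the log rule leaves the primary endpoint without a usable analysis. The rule applies only if % change is judged non-normal, and nothing in the protocol suggests that it will be. BMD itself is strictly positive, so the ANCOVA already planned on it could be log-transformed. The sentence may also have been meant for measured values only.

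**Conclusion.** The point holds as a modest improvement to consider. The deciding analysis omits a baseline value that the protocol collects and adjusts for elsewhere, so a chance imbalance can enter the headline estimate. For an imbalance of 0.3 SD, the effect is 0.05 to 0.41 points against a planned 4.9. This rests on 28 completers per arm, a common SD of 5.2, and correlations of -0.03 to -0.26 that are assumed. The shift is proportional to the correlation, so a stronger one would raise it. The gain is protection from chance imbalance and consistency with the other analyses.

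The log-transform point is secondary and conditional: it is a wording gap on a literal reading. The 64% and 28% figures themselves assume normality, so they show that negative values will be common, not that the rule will be triggered.

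**What to change.** In the Statistics section, make the primary analysis a linear model (ANCOVA) of % change in total hip BMD on treatment, with baseline total hip BMD as covariate, reported as an adjusted difference with a 95% CI. Keep the unadjusted t-test as a sensitivity analysis. The endpoint, scale and sample-size basis do not change.

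Limit the log-transform rule to strictly positive outcomes. State that, if % change is judged non-normal, log(18-month BMD) adjusted for log(baseline BMD) will be used.

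The cost is two sentences in the protocol and matching wording in the statistical analysis plan before data lock, with no new data, visits or participants. The headline becomes a baseline-adjusted difference and one degree of freedom is spent. Variance rises by up to about 2% if the correlation is below about 0.14 in size.
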